Different Conbercept Injection Methods in Treatment of Severe Proliferative Diabetic Retinopathy

NCT02816710 2016-06-30

Study Protocol

1. Study objectives:

To evaluate the clinical efficacy of preoperative, intraoperative or preoperative combined with intraoperative intravitreal conbercept (IVC) in vitrectomy with silicone oil tamponade for severe PDR patients.

2. Study design:

This is a prospective, open-labelled, randomized controlled trial to assess the clinical efficacy of preoperative, intraoperative or preoperative combined with intraoperative IVC injection in pars plana vitrectomy (PPV) with silicone oil tamponade for patients with severe proliferative diabetic retinopathy (PDR). The study was registered on 25 June 2016 (as NCT02816710).

3. Participants:

2.1 inclusion criteria:

- 1. Subjects of either sex aged \geq 18 years.
- 2. Diagnosis of diabetes mellitus (type 1 or type 2);
- 3. Active proliferative diabetic retinopathy was clinically evident;

4. Study eyes required a vitrectomy and silicone oil tamponade due to vitreous hemorrhage with significant fibrous proliferation, tractional retinal detachment in the posterior pole or complicated retinal detachment, which can be detected by B-scan ultrasonography.

- 5. Ability to give informed consent.
- 2.2 exclusion criteria:
- 1. Coexistent ocular disease that may interfere with visual outcome;
- 2. Prior vitreoretinal surgery or anti-VEGF pharmacotherapy in either eye;
- 3. A macula-involving retinal detachment for >6 months in the study eye;
- 4. Iris or angle neovascularization and neovascular glaucoma;

5. known allergy to any components of conbercept formulation

6. severe external ocular infection;

7. pregnancy or current oral contraceptive intake;

8. usage of anticoagulant or antiplatelet therapy;

preoperative or postoperative poor diabetes control [serum hemoglobin A1c (HbA1c) >11.0%];

10. uncontrolled systemic diseases, such as hypertension, cardiac diseases or presenting abnormal coagulation-associated blood diseases;

11. <6 months of follow-up post initial surgery.

4. Randomization:

Patients were recruited at the department of Ophthalmology, Ruijin Hospital, affiliated with Shanghai Jiaotong University School of Medicine, between July 2016 and September 2017, after approval of the local ethics committee. The use of conbercepts were discussed with patients, who all gave their written informed consent to undergo the procedure, after having been provided with a detailed description of the treatment. Eligible subjects after enrollment were randomized into one of the three possible treatment groups. Randomization was performed by an automated system at a 1: 1:1 ratio to 1 of 3 treatment arms: Group A received IVC (0.5 mg/0.05 mL) 3–5 days before PPV, while Group B received IVC (0.5 mg/0.05 mL) at the end of PPV. Group C received an IVC injection 3 to 5 days before PPV as well as an IVC injection at the end of operation.

5. Interventions:

Injections were administered according to the product recommendations and different time points under controlled aseptic conditions using sterile gloves, a sterile drape and a sterile eyelid speculum. Adequate topical anesthesia together with a broad-spectrum microbicide were administered prior to injection. All patients underwent 23-gauge transconjunctival suture-less vitrectomy using a 23-gauge trocar and cannula system. Simultaneously, phacoemulsification and aspiration (PEA) were performed in patients with cataracts, and an acrylic foldable intraocular lens (IOL) was placed in the capsular bag. During the operation,

hemostasis was maintained by endodiathermy. After vitrectomy, the vitreous body, preretinal fibrovascular tissue and tractional membranes were removed using a combination of segmentation and delamination techniques. If subretinal fibrotic bands were present, these bands were removed through retinotomy with subretinal forceps. The surgical endpoint was relief of traction on the macula and neovascular fronds that allowed the entire retinal to flatten, with silicone oil tamponade subsequently.

6. Assessments:

Included patients were followed at 1 day, 1 week, 1 month, 3 months, and 6 months after the operation. At baseline, the measurements included: a complete ophthalmological examination, with BCVA evaluated using logMAR visual acuity measurement, intraocular pressure (IOP), previous history of PRP, lens status, preoperative iris neovascularization, surgical indications. During surgery, the extent of vitreoretinal adhesion, degree of intraoperative bleeding, frequency of electrocoagulation, surgery duration and combined lens extraction were recorded carefully. At each time point during postoperative follow-up, incidence of recurrent VH, preretinal blood absorption time, BCVA, IOP, rubeosis, NVG, TRD, reoperation rate and systemic adverse events were evaluated respectively.

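### Exclusion criterion 11 (under 6 months of follow-up) can only be judged after randomisation; followed as written, it removes randomised patients together with data already collected

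*Protocol*

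**What the plan says.** Protocol section 3, in the exclusion list numbered 2.2, ends with "11. <6 months of follow-up post initial surgery". The HbA1c item in the same list excludes "preoperative or postoperative poor diabetes control [serum hemoglobin A1c (HbA1c) >11.0" per cent.

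Section 4 (Randomization) puts eligibility first and allocation second: "Eligible subjects after enrollment were randomized into one of the three possible treatment groups". Groups A and C then receive their allocated injection three to five days ahead of vitrectomy, so allocation must precede surgery. Section 5 (Interventions) states "All patients underwent 23-gauge transconjunctival suture-less vitrectomy using a 23-gauge trocar and cannula system".

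Section 6 (Assessments) sets the schedule: "Included patients were followed at 1 day, 1 week, 1 month, 3 months, and 6 months after the operation". It also says "During surgery, the extent of vitreoretinal adhesion, degree of intraoperative bleeding, frequency of electrocoagulation, surgery duration and combined lens extraction were recorded carefully". The postoperative outcomes, including "reoperation rate and systemic adverse events were evaluated respectively", are collected at each visit.

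The SAP names its tests (chi-square, ANOVA with Tukey, Kruskal-Wallis with Mann-Whitney). It defines no analysis population and has no intention-to-treat statement or rule for incomplete follow-up.

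**The concern.** An exclusion criterion should rest on facts available when the patient is randomised. Criterion 11 rests on a fact known only six months after surgery. Applied literally, it makes the analysed groups completers, selected by something that happened after allocation. The trial is open-label, so staying in follow-up may depend on arm as well as outcome. If loss is related to outcome differently by arm, the completers comparison is biased.

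Two consequences do not depend on why patients leave. Operative outcomes are complete on the day of surgery, so discarding them for a later loss to follow-up is wholly avoidable. And a patient who dies before six months meets the exclusion, so under the literal rule such deaths would count as zero in every arm, whatever their true number. A systemic adverse event that led a patient to leave early would go the same way.

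The words *or postoperative* in the HbA1c criterion repeat the fault. That part is secondary: it has no time window and section 6 lists no HbA1c measurement, so how often it would apply is unknown.

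**Working it through.** **Order of events**

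1. Eligibility is settled, then the patient is randomised (section 4).
2. Groups A and C receive the preoperative injection; vitrectomy follows (sections 4 and 5).
3. Operative data are recorded at surgery. Four of the five postoperative visits fall before month 6 (section 6).
4. Only at month 6 can criterion 11 be assessed.

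The *initial surgery* cannot be an earlier vitrectomy, because exclusion 2 bars prior vitreoretinal surgery. Nothing in section 6 or the SAP returns excluded patients to the analysis.

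**Size**

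The documents give no sample size, event rate or loss rate, so there is no planned figure to reproduce and every input below is assumed. Let p be the true risk in an arm, e the share lost before six months and q the risk among those lost. The risk seen in completers is

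c = (p − e·q)/(1 − e).

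*Operative outcome, p = 30% in both arms (say, marked bleeding).* Example: (0.30 − 0.20 × 0.60)/0.80 = 22.5%.

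| First arm (e, q) | Second arm (e, q) | Completers | Difference (points) | All operated |
|---|---|---|---|---|
| 15%, 30% | 5%, 30% | 30.0% v 30.0% | 0 | 0 |
| 10%, 50% | 10%, 50% | 27.8% v 27.8% | 0 | 0 |
| 10%, 50% | 10%, 30% | 27.8% v 30.0% | -2.2 | 0 |
| 15%, 50% | 5%, 50% | 26.5% v 28.9% | -2.5 | 0 |
| 15%, 50% | 5%, 30% | 26.5% v 30.0% | -3.5 | 0 |
| 20%, 60% | 5%, 60% | 22.5% v 28.4% | -5.9 | 0 |
| 20%, 60% | 5%, 30% | 22.5% v 30.0% | -7.5 | 0 |
| 20%, 10% | 5%, 30% | 35.0% v 30.0% | +5.0 | 0 |

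With low loss the effect is small. At 2% lost in each arm, with q = 50% to 60% in the first and 30% in the second, the difference is -0.4 to -0.6. At 5% v 2% lost it is -1.1 to -1.6. Standard errors widen by 1/√(1 − e) − 1, which is 2.6%, 5.4% or 11.8% for e = 5%, 10% or 20%.

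*Postoperative event, p = 25% in both arms.* Assume loss just after the 3-month visit and half of completers' events by then. Let f be the share of lost patients' events seen before loss. A time-to-event estimate using everyone is

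1 − (1 − E)·(1 − 0.5c/(1 − 0.5c)), where E = (1 − e)·0.5c + e·q·f.

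Example for e = 20%, q = 60%, f = 0.5: c = 16.25%; E = 0.065 + 0.060 = 0.125; 0.08125/0.91875 = 0.0884; estimate = 1 − 0.875 × 0.9116 = 20.24%.

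| First arm (e, q) | Second arm (e, q) | Completers difference | Time-to-event difference, f = 0.5 |
|---|---|---|---|
| 15%, 25% | 5%, 25% | 0 | 0 |
| 10%, 60% | 10%, 60% | 0 | 0 |
| 10%, 60% | 10%, 25% | -3.9 | -2.2 |
| 15%, 60% | 5%, 60% | -4.3 | -2.4 |
| 20%, 60% | 5%, 25% | -8.75 | -4.8 |
| 20%, 10% | 5%, 25% | +3.75 | +2.2 |

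The gap between the last two columns, at most 8.75 − 4.76 = 3.99 points, is what discarding already-seen events adds. The remainder is informative loss, which the repair does not remove. The repair can also do harm: if none of the first arm's lost patients have their event before loss (f = 0), -8.75 becomes -10.2.

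*Equal loss is not automatically safe.* With true risks of 25% and 15% and (10%, 60%) in both arms, completers show 21.11% v 10.0%, a difference of 11.1 points instead of 10.

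**The case against.** The strongest reply is that criterion 11 sits in an eligibility list, that eligibility precedes randomisation, and that it therefore means patients not expected to be available for six months. That would be an ordinary baseline criterion needing one clarifying phrase. No passage says that any randomised patient was removed. This reading is plausible, but the wording refers to follow-up actually achieved and nothing in either document settles the matter. If the benign reading was intended, one reworded sentence secures it.

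Other points stand as limits. Death is not a listed outcome, and systemic adverse events are assessed at every visit, so the loss of deaths and early adverse events holds only if safety reporting uses the same restricted set; the documents do not say which set it uses. The larger operative figures assume outcome-related loss in one arm only; with the same risk among the lost in both arms, or with low loss, they shrink as tabulated. The largest event figure is not attributable to criterion 11 alone. Mixed models and time-to-event methods are reasonable options, not the only correct ones. Section 4 describes recruitment in the past tense, so rewording eligibility may no longer affect who enters.

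None of this removes the defect: read literally, the criterion cannot be applied when eligibility is decided.

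**Conclusion.** The concern holds. Criterion 11 is wrong as written, and it bears on who is analysed in every comparison, so it must be corrected. Confidence is high for the wording defect and low for the size of its effect. If loss is unrelated to outcome in each arm, the between-arm difference is unbiased and the cost is precision only. If loss is related to outcome differently by arm, the bias can take either sign. In the assumed scenarios it reaches 7.5 points for operative outcomes, all of it due to the criterion. For postoperative events it reaches 8.75 points, of which no more than about 4 comes from throwing away events already observed. The actual size and direction cannot be determined from the documents.

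**What to change.** Delete criterion 11, or reword it as expected availability for six months judged before randomisation. Delete *or postoperative* from the HbA1c criterion. If enrolment is closed, the analysis and reporting changes below still apply.

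In the SAP, state that all randomised patients are analysed in their assigned arm:

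- Operative outcomes: everyone operated on.
- BCVA and IOP: all available visits, for example by a mixed model.
- Events: a method that allows for unequal follow-up, such as time-to-event by visit interval with censoring at last contact, or incidence rates. A simple proportion counted to last contact will not do: with unrelated loss of 15% v 5% it gives 23.1% v 24.4%, a spurious -1.25 points.
- Deaths and systemic adverse events: all randomised patients.
- Losses, and any randomised patients not operated on (possibly none, given section 5): by arm and reason.

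Keep the completers analysis as a sensitivity analysis. Add best- and worst-case bounds, because these methods still assume uninformative loss. With equal observed risks of 25% in those followed, the bounds are ±5 points at 5% lost per arm and ±10 at 10%.

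The cost is protocol and SAP wording, a little more analysis and some missing 6-month values to handle. No additional patients or visits are needed.

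### No harm assessment is described between the preoperative injection and surgery, so the first days after injection go uncounted in Groups A and C but not in Group B

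*Protocol*

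**What the plan says.** Protocol section 4 randomises patients after enrolment, 1:1:1, to three injection timings:

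- Group A: "Group A received IVC (0.5 mg/0.05 mL) 3–5 days before PPV".
- Group B: "Group B received IVC (0.5 mg/0.05 mL) at the end of PPV".
- Group C: "Group C received an IVC injection 3 to 5 days before PPV as well as an IVC injection at the end of operation".

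Protocol section 6 then describes three blocks of assessment. The first is a baseline examination. The second covers the operation itself: "During surgery, the extent of vitreoretinal adhesion, degree of intraoperative bleeding, frequency of electrocoagulation, surgery duration and combined lens extraction were recorded carefully". The third is follow-up: "Included patients were followed at 1 day, 1 week, 1 month, 3 months, and 6 months after the operation". The harms belong to this third block, whose timing is worded as "At each time point during postoperative follow-up". What is assessed at those visits reads: "incidence of recurrent VH, preretinal blood absorption time, BCVA, IOP, rubeosis, NVG, TRD, reoperation rate and systemic adverse events were evaluated respectively".

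Exclusion criterion 11 (protocol, section 2.2) removes patients with "<6 months of follow-up post initial surgery". The SAP defines no safety population, no adverse-event window and no rule for events before surgery.

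**The concern.** Injection timing is what the trial randomises, yet the clock for harms starts at the operation, not at randomisation or at the first injection. For Group B the two nearly coincide, because the injection is given at the end of surgery and visits follow at 1 day and 1 week. For Groups A and C the first injection comes 3–5 days earlier, and nothing in section 6 describes looking for harm in that interval.

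The early period after an injection is thus observed in one arm, unobserved in another and half observed in the third. A table of IOP problems, detachments or systemic events by arm would compare groups with different starting points relative to treatment. A patient whose event stopped the operation from going ahead would not appear in it at all.

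**Working it through.** The documents give no sample size, event rates or safety calculation, so there is no planned figure to reproduce. The check sets the schedule against the injection times.

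**Inputs.** From section 4: allocation 1:1:1; A has one injection 3–5 days before surgery; B has one at the end of surgery; C has both. From section 6: visits at 1 day, 1 week, 1, 3 and 6 months after surgery, with harms listed at those visits.

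**Step 1: time from an injection to the first described harm assessment.**

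- Preoperative injection (A, and C's first): 3 + 1 = 4 days to 5 + 1 = 6 days.
- Injection at the end of surgery (B, and C's second): 1 day.

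**Step 2: share of injections with no harm assessment described in the first days.**

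| Arm | Injections per patient | Preoperative | Share unassessed |
|---|---|---|---|
| A | 1 | 1 | 1/1 = 100% |
| B | 1 | 0 | 0/1 = 0% |
| C | 2 | 1 | 1/2 = 50% |

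Taking one patient per arm, 2 of 4 planned injections (50%) and 2 of 3 patients (67%) are affected.

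**Step 3: length of the gap.** Taking 6 months as about 183 days (an assumption), the gap is 3/(3 + 183) = 1.6% to 5/(5 + 183) = 2.7% of the time from first injection to the last visit in A and C. It is a small share of the calendar, but it is the period immediately after the injection.

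**Step 4: whether another block covers the gap.**

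- *Intraoperative block.* It holds surgical measures: adhesion, bleeding, electrocoagulation, duration and lens extraction. None asks about harms since the injection.
- *Baseline block.* It includes IOP and iris neovascularisation, but the protocol does not say whether baseline comes before or after the preoperative injection. If before, it cannot record a harm of that injection. If after, an early harm in A or C could be entered as a baseline finding.
- *Postoperative block.* A harm still present after surgery can be seen at the 1-day visit. A transient one, or one dealt with at surgery, need not be. Section 5 makes relief of traction and flattening of the retina the surgical endpoint, so traction that worsened beforehand need not show up as postoperative detachment.

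**Step 5: patients who do not reach surgery.** They have no visit in section 6. Exclusion 11 counts follow-up from the initial surgery, so on its face they have less than the required 6 months and are removed.

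**Step 6: the same interval in Group B.** Group B eyes have active disease and receive no conbercept until the end of surgery. Progression, bleeding or systemic events while these patients wait are not counted either. The asymmetry shown in Steps 1 and 2 therefore concerns harms caused by the injection, not all events before surgery.

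**The case against.** The strongest reply has five parts.

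- **Silence is not prohibition.** Section 6 says what was evaluated at the postoperative visits and does not forbid recording other events. That is so, and the gap is inferred from what is not described. But no visit, form or analysis is described that would count such events, and informal capture in an open-label trial does not ensure equal ascertainment across arms.
- **Not every outcome starts after the operation.** A reader might infer that from the visit schedule. The documents do not support it: bleeding, electrocoagulation and surgery duration, on which a preoperative injection would be expected to act most directly, are recorded during surgery. The point is confined to harms.
- **The omission need not favour A and C.** A reader might infer that it can only hide harms of the preoperative injection. Step 6 shows otherwise. If conbercept reduces events before surgery, leaving the interval out hides events in Group B and works against A and C. This part stands in full. It also means that a count of missed events in A and C set against none in B would hold only for injection-caused harms, and would need rates and a sample size that the documents do not give.
- **The stated objective is efficacy.** Section 1 names only clinical efficacy, and neither document defines a formal safety comparison. That lowers the stakes. Even so, section 6 lists these harms as evaluated outcomes, and if they are compared between arms they need a common starting point.
- **No cancelled surgery is described.** Section 5 says that all patients had vitrectomy, and exclusion 11 does not mention patients without surgery. Their removal is a reading of the wording, not a stated rule. The wider problem of excluding patients after randomisation is a separate matter.

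**Conclusion.** The point holds for harms. As written, the plan describes no harm assessment in the 3–5 days between the preoperative injection and surgery. That leaves the first days unassessed after all of Group A's injections and half of Group C's, while Group B's are covered by the 1-day and 1-week visits. What would be lost are harms that are transient, resolved at surgery or serious enough to prevent it. Persistent harms may still be seen afterwards.

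The net direction and size of any bias cannot be computed, because Group B's events before surgery are uncounted too and no event rates or sample size are given. The conclusion rests on taking section 6 as the full account of what was collected and on reading exclusion 11 literally. It is a cheap and worthwhile improvement to the comparison of harms. It does not show that the efficacy comparison is wrong.

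**What to change.** In protocol section 6:

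1. Count ocular and systemic events from randomisation, not from the operation, in all three arms.
2. At the surgery contact, record any such event since randomisation in A, B and C alike. No examination on the day of surgery is described at present, so the text must state this.
3. Report the interval from randomisation to surgery by arm. The protocol gives none for Group B, and counting from a common start is fair only if the reader can see whether the windows are of similar length.
4. Keep randomised patients whose surgery did not take place in the safety counts, and say that exclusion 11 does not remove them from those counts.
5. State whether baseline is measured before the preoperative injection.

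The SAP should name the matching safety population and event window. The cost is a few sentences, a few extra form fields and slightly more data entry. No treatment changes. If data are already collected, events between randomisation and surgery can be sought in hospital records for all three arms, and the limitation stated in the report.

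### Apart from a short list of complications, ocular adverse events are not prespecified for recording, although one arm is scheduled for two injections and the others for one

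*Protocol*

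**What the plan says.** Protocol section 6 (Assessments) sets the visits: "Included patients were followed at 1 day, 1 week, 1 month, 3 months, and 6 months after the operation". The items for each visit begin "At each time point during postoperative follow-up, incidence of recurrent VH, preretinal blood absorption time" and continue "BCVA, IOP, rubeosis, NVG, TRD, reoperation rate and systemic adverse events were evaluated respectively". A separate list in the same section covers what is noted during surgery: adhesion, bleeding, electrocoagulation, duration and combined lens extraction.

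Section 4 (Randomization) allocates patients "at a 1: 1:1 ratio to 1 of 3 treatment arms". The arms are: "Group A received IVC (0.5 mg/0.05 mL) 3–5 days before PPV, while Group B received IVC (0.5 mg/0.05 mL) at the end of PPV". The third is: "Group C received an IVC injection 3 to 5 days before PPV as well as an IVC injection at the end of operation".

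Section 5 (Interventions) describes injection "under controlled aseptic conditions using sterile gloves, a sterile drape and a sterile eyelid speculum". For subretinal fibrotic bands it says that "these bands were removed through retinotomy with subretinal forceps". Inclusion criterion 4 admits eyes with complicated retinal detachment as well as tractional detachment.

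The SAP names no safety variable and no safety analysis. Its generic chi-square test for categorical variables is the only method that would apply to event counts.

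**The concern.** The number of intravitreal injections is part of the randomized contrast. Group C differs from Group B by the preoperative injection, and from Group A by the injection at the end of surgery. A reader who wants to know whether the extra injection is worthwhile needs its local harms beside its effect on bleeding and vision.

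The section 6 list gives part of that. The ocular items it names are mainly complications of the retinopathy. The one category that could take in anything unforeseen is closed to the eye by the word systemic. Detachment is recorded only if tractional, although eyes with other forms may be enrolled and retinotomy is part of the described surgery. A site that followed the list exactly could compare one injection with two and have no prespecified place to record an infected or inflamed eye.

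**Working it through.** The documents give no sample size, event rate or safety figure, so there is no stated number to reproduce. The check is a comparison of texts, followed by a little arithmetic on what can and cannot be said about size.

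**1. Which ocular events are listed**

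| Event | In section 6 or the SAP? | Other route by which it might show |
|---|---|---|
| Recurrent vitreous haemorrhage | Yes | n/a |
| IOP, rubeosis, neovascular glaucoma | Yes | n/a |
| Tractional detachment | Yes | n/a |
| Endophthalmitis | No | BCVA, without identifying it; reoperation if operated on |
| Intraocular inflammation | No | BCVA or IOP, without identifying it; reoperation if operated on |
| Lens injury | No | BCVA, without identifying it; reoperation if operated on |
| New retinal break | No | Reoperation if operated on |
| Non-tractional or combined detachment | No | BCVA, without identifying it; reoperation if operated on |

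Reoperation is recorded as a rate, and no cause is asked for. The intraoperative list does not contain the missing items either.

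**2. Injections per eye (section 4)**

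A = 1, B = 1, C = 1 + 1 = 2.

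**3. When recording starts (section 6)**

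Every follow-up visit is counted from the operation. In Groups A and C the preoperative injection comes 3 to 5 days earlier, and no visit is listed in that interval.

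**4. Expected ratio between arms**

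Let s be the risk of a given event from the surgery common to all arms, and p the added risk per injection, taken as small and equal for both injection times. Then

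risk in A or B ≈ s + p; risk in C ≈ s + 2p; ratio = (s + 2p)/(s + p) = 1 + p/(s + p).

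- s = 0: ratio = 2.
- s = p: ratio = 3/2 = 1.5.
- p = 0 (a purely surgical event): ratio = 1.

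The ratio therefore lies between 1 and 2 and reaches 2 only when surgery contributes nothing. The documents give neither s nor p.

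**5. What recorded zeros would tell the reader**

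With 0 events among n eyes, the one-sided 95% upper bound is 1 − 0.05^(1/n). The arm sizes below are assumed.

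- n = 30: 1 − 0.05^(1/30) = 9.5%.
- n = 50: 1 − 0.05^(1/50) = 5.8%.
- n = 80: 1 − 0.05^(1/80) = 3.7%.

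These bounds do not measure the defect. They show that a recorded zero, though weak, can be interpreted, while an event that was never asked about cannot.

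**The case against.** The objective in section 1 is efficacy only, and the plan does record ocular harm: recurrent haemorrhage, IOP, rubeosis, neovascular glaucoma, tractional detachment and reoperation. BCVA would also fall with serious local harm. This stands, and it rules out one tempting inference, that ocular harm goes uncollected or that a report would show no local harm in any arm. The gap is confined to the unlisted events.

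Three other inferences also go too far.

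- *Unlisted events would never be counted.* That reads silence as prohibition. The documents support only that these events are not prespecified.
- *Group C would have twice the harm.* Every arm has vitrectomy with silicone oil, and some eyes have lens surgery. These can cause infection, inflammation, lens injury or breaks regardless of injection count. A redetachment through a retinotomy is a surgical event.
- *The documents themselves name these as treatment risks.* Exclusions 5 and 6 (known allergy, existing external infection) are eligibility rules. Aseptic technique and retinotomy are descriptions of procedure.

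It is also fair to say that such events may be too few to compare. That argues for intervals rather than tests; it does not argue for leaving the events out. Nor does the efficacy objective settle the matter: the plan chose to collect adverse events and then limited the category to those away from the injected eye.

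**Conclusion.** The concern holds in a limited form. Selected ocular complications are recorded, but the open-ended adverse-event category covers systemic events only, and detachment covers the tractional kind only. Five kinds of event (endophthalmitis, intraocular inflammation, lens injury, new retinal break, non-tractional or combined detachment) have no prespecified place. They would surface only as an unexplained reoperation, if at all.

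The efficacy comparisons are not invalidated. What is lost is the ability to weigh the local harm of the second injection against its benefit. The size of any difference between arms cannot be quantified from the documents. The 1-to-2 range for the ratio assumes small, additive risks that are equal for the two injection times, and the bounds for zero events rest on assumed arm sizes. The change should be made, because it affects the benefit-risk reading of the main contrast and costs little.

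**What to change.** In Protocol section 6:

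- Replace the systemic category with *all ocular and systemic adverse events from the first study procedure (injection or surgery)*, with endophthalmitis, intraocular inflammation, lens injury and new retinal break as prespecified terms. Starting at the first procedure brings in the 3 to 5 days before surgery in Groups A and C.
- Replace TRD with *any retinal detachment, classified as tractional, rhegmatogenous or combined*.

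In the SAP, report each event by arm as n/N with an exact confidence interval. A further split by scheduled number of injections adds little, because arm already fixes that number at 1, 1 and 2.

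The cost is a few form fields and possibly a less favourable safety table. The items already required at each visit imply that the eye is examined. However, section 6 names a complete eye examination at baseline only, so the sponsor should confirm that the follow-up examination is sufficient to detect a break and classify a detachment. No dose, schedule or treatment rule changes.
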